Prior to the baseline assessment, parents will be randomly assigned by the Data Manager to either the behavioral parent training group with a mindfulness component (BPT-M) or an education component (BPT-E) by means of a random numbers table. An approximately equal distribution of families will be assigned to each of the two conditions. Families will be told of their condition assignment at the end of the observation task in the baseline visit.

Cohort 2

Recruitment methods are described below in section D. Interested parents will either contact the PRO-Parenting Project by phone or by completing a form on our project website. If the family indicates interest in participation, trained staff will conduct a phone screen (“Cohort 2 Script for initial contact phone screen” and “Cohort 2 script clinical screen baseline”). If the family meets eligibility for the study, they will be mailed an assessment packet, consent form, and return envelope, and will be scheduled for a series of 3 remote appointments for the purposes of baseline data collection (“Cohort 2 script for confirmation call to schedule remote home visit”). Information gathered from the initial screening calls will be destroyed for families who do not meet eligibility requirements, as well as for those who do meet requirements but choose not to participate. For families who proceed to the study, information gathered from the screening call will be used to assess parenting stress, which is a variable of interest to this study.

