Prior to the baseline assessment, parents will be randomly assigned by the Data Manager to either the behavioral parent training group with a mindfulness component (BPT-M) or an education component (BPT-E) by means of a random numbers table. An approximately equal distribution of families will be assigned to each of the two conditions. Families will be told of their condition assignment at the end of the observation task in the baseline visit.

Parent Groups

Cohort 1

For our first cohort, two parent groups were run concurrently and face-to-face at King School in Oregon City, OR (this facility is a former elementary school managed by the Clackamas ESD for HeadStart classes and early childhood special education classes) until the COVID-19 pandemic forced the CESD to close the building on March 12, 2020. Prior to the building closure, childcare was offered during all sessions and provided by staff who worked at the ESD, who had experience working with children with DD, and who were willing to work for our project as a paid second job. After the building closure, the two parent groups for Cohort 1 were run as virtual meetings through the Zoom platform, and no childcare was provided.

Cohort 2

For our second cohort (and any later cohorts), the two parent groups will be run 100% as virtual meetings through the Zoom platform and no childcare will be provided. All materials required for participation in parent groups will be mailed to parents prior to the first session.

Both Cohorts

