The BPT-M group and the BPT-E groups will be led by staff with a minimum of a Masters-level education in clinical or counseling psychology or social work. These individuals will be trained and supervised by a doctoral-level licensed psychologist. Parents randomly assigned to the BPT-M group will receive six sessions of Mindfulness-Based Stress Reduction followed by the 10-week BPT intervention described below. The MBSR component of the BPT-M intervention will include six weekly 2-hour group sessions and 30-45 minutes of daily home practice guided by instructional audio CDs and an MBSR parent workbook (see “Baer Mindfulness Home Practice Log” for sample homework for the Mindfulness group). Formal mindfulness exercises aim to increase the capacity for mindfulness (present moment awareness with a compassionate, nonjudgmental stance) and include a body scan, mindful yoga, and sitting meditation. In the sessions, participants practice formal mindfulness exercises and ask questions relating to the practice of mindfulness in everyday life, and the instructor provides didactic instruction on stress physiology and using mindfulness for coping with stress in daily life.

Parents randomly assigned to the BPT-E group will receive six sessions of education about children with developmental delays. The BPT-E group will also consist of 6-weekly 2-hour education sessions where families will gain information regarding their child's development, disability, and associated considerations. Each week has a general topic for discussion. Topics include Preparing for Individualized Education Plan (IEP) meetings, Navigating regional service agencies, communicating with Teachers, Advocacy, Sibling Issues, and Community Resources. At the start of each session, group leaders provide some didactic material on the topic. Parents then break up into pairs for small group discussion (via “breakout rooms” when groups conducted via Zoom) followed by a larger group discussion and questions. Parents in this group will also receive homework each week (see “BPT-E Hand Out Session 2”). Following the 6-week educational intervention, families will receive the same 10-week Behavioral Parent Training intervention described below.

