All participants will then receive the Incredible Years Parent Training-Developmental Disabilities modified intervention. The IYPT-DD intervention is 10 weeks in duration, with each weekly session lasting 2 hours. Each weekly session is structured around videotape vignettes and uses discussion, role-playing, modeling, and feedback techniques to create an effective learning environment for the parenting skills that are taught. Topics include: using developmentally appropriate play to engage children, using praise and rewards to encourage children's development, and using effective behavior management strategies to reduce challenging behavior. Parents are given weekly homework assignments and have the opportunity to practice their skills both inside and outside of intervention sessions (see “Hand Out BPT Session 1 Play Time”).

All participants, regardless of treatment condition, will complete a brief Subjective Units of Distress Scale (SUDS; see “PP-PDX-tx-SUDS”) at the beginning of each session and a weekly evaluation form at the end of each session (see “PP-PDX-tx-PWE-s1-6” and “PP-PDX-tx-PWE-s7-16”). For Cohort 1, these forms were collected via

Teleform surveys when groups met face-to-face. Once parent groups shifted to a virtual format, these forms were collected via Qualtrics. These forms will continue to be collected via Qualtrics in Cohort 2 and future cohorts. Participants will also complete a survey packet at the end of week 6 (see “PP-PDX-tx-PSI4”, “PP-PDX-tx-FFMQ”, and “PP-PDX-tx-GROUPQuestionnaire”), and at the end of week 16 during group time (see “PP-PDX-tx-PSI4”, “PP-PDX-tx-FFMQ”, “PP-PDX-tx-PCBC”, “PP-PDX-tx-GROUPQuestionnaire”, “PP-PDX-tx-PPSQ-E” and “PP-PDX-tx-PPSQ-M”; note the last two are very similar packets but one is for the BPT-M group and one is for the BPT-E group). During week 16, participants will also complete a brief telehealth satisfaction survey (see “Telehealth questions_final_6.4.2020”) via Qualtrics to assess their satisfaction with the parent groups/ interactions with group leaders after the transition to a remote format as a result of the COVID-19 pandemic. This questionnaire was slightly modified for cohort 2 to reflect the fact that this cohort did not transition to a remote format but instead did the entire intervention in a remote format (see “Telehealth questions_c2w2”).

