For Cohort 1, these data were initially collected via a phone interview lasting approximately 1 hour (see COVID-19 interview questions for PROParenting families_FINAL" and "COVID-19 survey questions for PROParenting families_4.14.20_Final") as a separate data collection activity in Spring 2020. Longitudinal data will be collected from this cohort via Qualtrics survey in Fall 2020 and at the time of 6-month and 12-month follow-up data collection as described above (see "impact of covid-19 survey for Qualtrics"). The Covid-19 survey collected at the 12-month follow-up will be slightly modified from the one given at earlier time points to have tighter time frames on questions (see "impact of Covid-19 survey for Qualtrics_rev2").

For Cohort 2, these data will be collected via Qualtrics survey at baseline and immediate follow-up data collection, as described above. At baseline, the completion of this Qualtrics survey will be facilitated by the family interventionist in an interview-format during the rapport building appointment; participants will complete it on their own at the time of immediate follow-up (see "impact of covid-19 survey for Qualtrics_rev2").

Data Analysis

Analyses will be conducted using standard normal theory regression and structural equation modeling (SEM) techniques, with a particular focus on latent growth modeling (LGM; Muthén & Curran, 1997). To isolate the added value of the MBSR component of the BPT-M intervention, primary intent-to-treat (ITT) efficacy hypotheses comparing the BPT-M with BPT-E will be specified within a set of sequential mediation analyses (DeGarmo, Patterson, & Forgatch, 2004). We will use CACE modeling (Jo, 2002; Little & Yau, 1998) for analyzing and adjusting effect sizes on the basis of participant compliance and dosage in both groups. CACE mixture models allow unbiased estimates of intervention contrasts by modeling unknown compliance status as missing data using the known compliance in the intervention of focus, thereby matching latent characteristics to the two group conditions. We will intentionally assess and control for potential confounding variables that pose a possible threat to the internal validity of the study, namely, child diagnosis (e.g., ASD), child IQ/intellectual disability status, child gender, concurrent child services, and demographic variables (e.g., ethnicity, family language, family structure, SES).

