For the primary main effects efficacy evaluation, BPT-M versus BPT-E, we will specify LGMs. For our primary intervention efficacy hypotheses, child outcomes are considered distal because they are not the primary active agent of intervention. Any BPT intervention effects on children are hypothesized to operate through, and be transmitted through, more-proximal mechanisms of reduced parenting stress, and in turn, improved parenting (Forehand, Lafko, Parent, & Burt, 2014). For growth outcomes, a sequential set of models tests the latent variances and model fit comparing a random intercept only versus linear growth or quadratic growth models to determine the optimal pattern of change (Duncan, Duncan, & Stryker, 2006). For example, we will test the hypothesis that the BPT-M will show greater 1-year reductions in child behavior problems relative to the BPT-E condition. This effect is hypothesized to be mediated first by improvements in effective parenting behaviors. Intervention impact on growth in positive parenting skills, in turn, is hypothesized to be mediated by reductions in parenting stress, the target of the E-BPT intervention.

For tests of mediation, we will use approaches outlined for SEM and LGM (Cheong, MacKinnon, & Khoo, 2001; Judd, Kenny, & McClelland, 2001; Kraemer, Wilson, Fairburn, & Agras, 2002; MacKinnon & Luecken, 2008), including tests of indirect effects following recommendations using bootstrapped standard errors for the asymptotically distributed multiplicative indirect terms and estimated bias-corrected confidence intervals (MacKinnon, Fairchild, & Fritz, 2007; Preacher & Hayes, 2008).

D. Research Population & Recruitment Methods

1. Participant Population:

Between the Oregon and California sites, we anticipate screening 300 families to recruit 230 children with DD and their families (n=150 in CA; n=80 in OR). This would result in roughly 115 participants in each of the treatment conditions, which will provide adequate statistical power to minimally detect modest to medium effects in our primary analyses. These effect sizes are conservative based on past research.

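### Families are randomised individually but treated in parent groups in both arms, and the planned models state no term or error structure for parent group

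*Combined protocol and SAP*

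**What the plan says.** Allocation is by family. Under Recruitment and Baseline Data Collection (section C), both cohorts carry the same sentence: "parents will be randomly assigned by the Data Manager to either the behavioral parent training group" with mindfulness or with education, using a random numbers table.

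Delivery is by group in both arms. Under Parent Groups, "The BPT-M group and the BPT-E groups will be led by staff with a minimum of a Masters-level education". The mindfulness component is "six weekly 2-hour group sessions", and the education component has the same number and length of sessions. All families then have ten weekly sessions of behavioural parent training, which "uses discussion, role-playing, modeling, and feedback techniques to create an effective learning environment". For Oregon, the first cohort had two parent groups, and "For our second cohort (and any later cohorts), the two parent groups will be run 100% as virtual meetings through the Zoom platform".

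Data Analysis opens with "Analyses will be conducted using standard normal theory regression and structural equation modeling (SEM) techniques" and goes on to latent growth models, sequential mediation with bootstrapped indirect effects, and CACE mixture models. The growth models are chosen by "comparing a random intercept only versus linear growth or quadratic growth models to determine the optimal pattern of change"; that random intercept is a growth factor for repeated measures on a child, not a parent-group effect. The control variables are "child diagnosis (e.g., ASD), child IQ/intellectual disability status, child gender, concurrent child services, and demographic variables". Parent group, leader, cohort and site are not among them.

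Section D.1 plans 230 families (150 in California, 80 in Oregon), roughly 115 per arm. It calls power adequate for effects of modest to medium size and gives no alpha, numeric effect size, ICC or group size.

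**The concern.** Families in the same parent group share a leader, peers and group discussion for 16 weeks after randomisation. This is an individually randomised group-treatment design with grouping in both arms. If families in one group end up more alike than families in different groups of the same site and cohort, each arm mean carries group-to-group variation that an independent-families model leaves out. The standard error of the BPT-M versus BPT-E contrast is then too small, and so are those of the arm-to-mediator paths that feed the indirect effects. A bootstrap that resamples single families has the same fault. All three aims are affected. The mediators may be the more exposed, because parenting stress and parenting are what the groups work on directly.

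Correlation shared by a whole cohort, such as pandemic timing, falls on both arms and does not inflate the error of the contrast.

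**Working it through.** **Inputs from the documents.** 150 + 80 = 230 families; 230/2 = 115 per arm. Two parent groups per Oregon cohort.

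**Assumptions.** Two-sided 5% test; ICC 0.01, 0.02 or 0.05; group size m from 8 to 20. The range of m comes from Oregon's 80 families in two groups per cohort: 80/(2 × 2) = 20, 80/(2 × 3) = 13.3, 80/(2 × 4) = 10 and 80/(2 × 5) = 8. Two cohorts are described for Oregon, and 5 is the highest cohort number named. Applying this range to all 230 families is an assumption, because California's groups are not described.

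**Benchmark under independence.** The power statement has no number to reproduce. With 115 per arm, the detectable standardised difference at 80% power is (1.960 + 0.842) × √(2/115) = 0.37.

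**Type I error when parent group is ignored.** The design effect is DE = 1 + (m − 1) × ICC, and the actual error is 2 × [1 − Φ(1.96/√DE)]. For a growth slope, ICC is multiplied by the slope reliability (the share of variance in the estimated slopes that is true slope variance), taken as 0.5. Example: m = 20, ICC 0.05 gives DE = 1 + 19 × 0.05 = 1.95 for a single time point and 1 + 19 × 0.025 = 1.475 for the slope.

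| ICC | Single time point, m = 8 / 12 / 20 | Slope, reliability 0.5, m = 8 / 12 / 20 |
|---|---|---|
| 0 | 5.0% / 5.0% / 5.0% | 5.0% / 5.0% / 5.0% |
| 0.01 | 5.8% / 6.3% / 7.2% | 5.4% / 5.6% / 6.1% |
| 0.02 | 6.6% / 7.6% / 9.5% | 5.8% / 6.3% / 7.2% |
| 0.05 | 9.2% / 11.5% / 16.0% | 7.1% / 8.3% / 10.7% |

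The slope column is nearer to the planned primary analysis, which is a growth model.

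**Check by simulation.** 20,000 runs per setting, no true effect, waves at 0, 4, 10 and 16 months, one group per arm per site-by-cohort block, slope ICC 0.05, reliability 0.5. The unadjusted test rejected in 7.3% and 8.5% of runs for groups of 8 and 12, close to the formula. With half of the correlation at cohort level it rejected in 6.0% and 6.6%, and with all of it there in 4.8% and 4.7%.

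**Power once groups are respected.** SE = √(2 × DE/115), noncentral t, 230/m groups in all, and half as many blocks if each block has one group per arm. Values are for a single-time-point contrast with m = 8 / 12 / 20.

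| Degrees of freedom | ICC | Detectable d, 80% power | Power at d = 0.5 | Power at d = 0.4 |
|---|---|---|---|---|
| Groups − 2 | 0.05 | 0.45 / 0.49 / 0.58 | 88% / 82% / 68% | 71% / 63% / 50% |
| Blocks − 1 | 0.05 | 0.46 / 0.52 / 0.66 | 86% / 77% / 58% | 68% / 58% / 41% |

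Under independence, power is 96.5% at d = 0.5 and 86% at d = 0.4. The blocks − 1 reference costs power even at ICC 0: with groups of 20 it gives about 84% at d = 0.5 and 67% at d = 0.4.

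**The case against.** The strongest reply is that harm is not shown. The documents give no ICC, and at ICC 0, or with all correlation at cohort level, the planned analysis holds its 5%. Children take no part in the intervention (section E), so correlation may be weakest for child behaviour, the Aim 1 outcome. This stands as a limit on the size. It does not justify assuming zero: the plan itself says that effects on children pass through parenting stress and parenting, so correlation there can carry through.

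Scope is a second limit. California's cohorts were run under protocols not included here, and 150 of the 230 families are there. One group per arm in each Oregon cohort is an inference from two groups and two arms, and whether leaders differ by arm is not stated.

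A reader might infer that the trial is underpowered, or that its false-positive rate will be as high as 16%. The documents support neither. The power statement has no figure to contradict, and in many of the scenarios above power at d = 0.5 stays near or above 80%. The 16% needs a single-time-point contrast, groups of 20, ICC 0.05 and all correlation at group level together.

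**Conclusion.** The omission is clear: individual randomisation, group treatment in both arms, and no term or error structure for parent group in the growth, mediation or CACE analyses, with site and cohort also absent from the control variables. Under any positive within-group correlation beyond site and cohort, following the plan as written gives standard errors that are too small. How much too small is conditional. For the growth-slope contrast with reliability 0.5 and groups of 8 to 20, type I error is about 5.4-6.1% at ICC 0.01, 5.8-7.2% at 0.02 and 7-11% at 0.05. For a single time point it is about 6-7%, 7-10% and 9-16%. Group size, ICC, reliability and the level at which correlation arises are all assumptions. The point should be fixed because the remedy is cheap, and an error structure chosen after the results are seen would leave the main contrast open to challenge.

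**What to change.** In Data Analysis:

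- State that the main-effect growth models, the mediation models and the CACE models account for parent group in both arms, by a group-level random effect or by cluster-robust errors with a small-sample degrees-of-freedom correction, and that they include site and cohort.
- Give the number of parent groups per arm in each site-by-cohort block. Where a block has one group per arm, say that group variance cannot be separated from arm-by-block variation, and use a small-sample reference distribution based on the number of groups or blocks.
- State that intervals for indirect effects also account for parent group and do not resample single families as if independent.

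In D.1, give the detectable effect at 115 per arm over a stated range of ICC and group size, using the same degrees of freedom as the chosen analysis.

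The cost is plan wording and a parent-group identifier for every family. Oregon records attendance at each parent group; an equivalent record must be confirmed for California. No extra families are needed. The downsides are wider intervals, lower power when groups are few (even at ICC 0, as shown above), and possible convergence difficulty in the CACE mixture models.

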This study has significant potential to improve the long-term well-being of children with DD and their families by determining the added benefit of targeting parenting stress and parent management strategies to more effectively reduce behavior problems among children with DD. Findings from this study will improve the scientific understanding of evidence-based interventions for behavior problems among children with DD and the mechanisms underlying therapeutic change.

B. Specific Aims/Study Objectives

Aim 1: Test the efficacy of BPT-M, which adds a parent stress-reduction intervention (MBSR), compared with BPT-E (BPT+ psychoeducational control), for reducing the distal outcome of child behavior problems.

Hypothesis 1: Children of parents who complete the BPT-M intervention will exhibit greater and more sustainable reductions in child behavior problems at posttreatment and at 6- and 12-month follow-up, compared with children whose parents participate in the BPT-E intervention, as evidenced by parent and teacher reports and observational measures of child behavior problems.

Aim 2: Examine if parenting behavior mediates the relation between intervention and child behavior problems.

Hypothesis 2: Changes in parenting behavior, as measured by self-report and observations, will mediate the relation between intervention and the reduction of child behavior problems at post-treatment and at 6- and 12-month follow-up.

Aim 3: Determine if the improvements in parenting behavior are, in turn, mediated by reductions in parenting stress, a proximal target of the BPT-M intervention.

Hypothesis 3: Improvements in parenting behavior will be mediated by a reduction of parenting stress immediately post-treatment and at 6- and 12-month follow up.

C. Methods, Materials and Analysis

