Prior to the second Zoom appointment, parents will receive a box of assessment materials in the mail intended to help facilitate the family observation task (see “c2 cover letter_baseline assessment kit” and “virtual play tasks instructions #2 sent in kit”). This box will include 3 puzzles and a play mat that will be used for the home visit; families may keep these items and add them to their child’s toy collection after the visit. The second Zoom appointment will involve a research assistant, the parent, and the target child. The purpose of the second appointment is to record the family observation task, a 20-minute videotaped play assessment between the parent and target child. At the beginning of this appointment research staff will go over the remaining instructions for the family observation task. The parent and child will then be asked to complete 3 tasks (see “C2 baseline play task script protocol”): (1) *Unstructured free play task* (parent is instructed to allow the child to choose any activity and play along with the child as they normally would); (2) *Clean-up task* (parent is instructed to give the child a command to clean up); and (3) *Parent teaching task* (parent is instructed to select an activity and to keep the child playing according to the parent’s rules). We will use established coding systems to evaluate parent and child behavior in these tasks (Simple Affect Code: Jabson & Dishion, 2004; Relationship Process Code: Jabson & Dishion, 2005; Parent-Child Behavior Observation System: Phaneuf & [name], 2007).

The third Zoom appointment is a rapport building appointment between the family interventionist and the parent and will be conducted via Zoom. At this appointment, the parent and family interventionist will complete the Change Plan Worksheet (see “BPT-E Change Plan Worksheet PEI baseline” and “BPT-M Change Plan Worksheet PEI baseline”; these forms are very similar but one is for participants in the BPT-E condition and one for those in the BPT-M condition). The family interventionist will also complete a Qualtrics COVID survey as an interview (see “Impact of covid-19 survey for qualtrics”) during this appointment to gather additional information about family stressors during this unique historical period. See “c2 PEI BPT-M Protocol script” for script for this

visit for participants assigned to the BPT-M group and “c2 PEI BPT-E protocol script” for participants assigned to the BPT-E group.

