Informed consent will be obtained at the first Zoom appointment (baseline assessment appointment 1) by the research staff. Parents will be mailed a copy of the consent form ("Informed consent_PRO-Parenting_10.7.20") with their packet of questionnaires. At baseline assessment appointment 1, the research assistant will present the consent video, which goes over each element of the consent form (see "Consent Script PP_final" and "informed consent slides_final"). Parents will be informed that group assignment is random and that they may be assigned to the Behavioral Parent Training-Mindfulness (BPT-M) group or the Behavioral Parent Training-Education (BPT-E) group. After the video, the research assistant will offer to answer any and all questions the parent(s) has and to address any concerns. Parents will be reminded that their consent is voluntary, that they can withdraw from the study at any point, and that they do not have to answer any question or participate in any task that they do not want to. Given the young age of the children in the study (ages 3 to 5), parents will consent for their children's participation. Again, children will only be involved in observation tasks at four virtual home assessments (at pre-intervention, post-intervention, 6-month, and 12-month follow-ups) to measure intervention outcomes, but will not be involved in the proposed intervention. Children will also be involved in the "lab visit" to complete the Stanford-Binet and ADOS-2 testing, but only if physical distancing and face covering restrictions are lifted during the study period. If restrictions are not lifted, we will forgo this piece of data collection.

Parents will be asked to sign their consent form if they have not already done so, and to provide verbal consent to participation in order to continue with the appointment. Research staff will have a copy of the consent form available to them via qualtrics. They will check a box to indicate that they have received verbal consent before proceeding with the rest of the appointment.

Both Cohorts

The PI for this project has had extensive training in conducting research with similar families and has a history of federally-funded randomized controlled prevention and early intervention trials. Staff working on the project will complete training with the PhD-level project coordinator on providing informed consent and administering the standardized protocol.

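### If the observed-behavior codes are skewed counts, the normal-theory tests that choose the growth shape can reject the true shape well above 5%; robust ML with scaled tests would largely cure this

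*Combined protocol and SAP*

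**What the plan says.** Section C, Data Analysis, sets the estimation framework in one sentence: "Analyses will be conducted using standard normal theory regression and structural equation modeling (SEM) techniques". For growth outcomes, the same section says "a sequential set of models tests the latent variances and model fit comparing a random intercept only versus linear growth or quadratic growth models". The shape that emerges is then used for the arm comparison.

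Hypothesis 1 (Section B) is to be judged "as evidenced by parent and teacher reports and observational measures of child behavior problems". Of the observational measures, the baseline procedures say only "We will use established coding systems to evaluate parent and child behavior in these tasks". The play task is described as 20 minutes at baseline and about 15 minutes at the virtual post-treatment visit.

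The plan does not give:
- the scale, skewness or kurtosis of any outcome;
- a robust estimator, scaled statistic, count model or transformation;
- the statistic, threshold or residual-variance structure for choosing the shape;
- the coding of time, or which growth parameter carries the arm effect.

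The one departure from normal theory is bootstrapping, and it is reserved for indirect effects. It does not touch the choice of shape.

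**The concern.** With two arms of similar size, a difference in means or slopes is fairly insensitive to skewness. Tests of variances and of covariance fit are not. Their normal-theory reference distribution is right only if the fourth moments are those of a normal distribution. With heavy tails the statistic is too variable and rejects too often.

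The plan uses that kind of test to decide how many growth factors to keep. Frequencies of problem behavior in a 15-20 minute task could plausibly be counts with many low values and a long right tail. A trial could then report curvature, or individual differences in slope, that reflect the distribution of the codes and not the course of child behavior. An unneeded quadratic factor also changes the meaning of the linear coefficient.

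**Working it through.** **1. The plan's own figure.** Section D.1 plans to "recruit 230 children with DD and their families (n=150 in CA; n=80 in OR"), and 150 + 80 = 230; 230/2 = 115, matching "roughly 115 participants in each of the treatment conditions". No effect size, alpha or power is given, so N cannot be derived. At two-sided 5% and 80% power the detectable difference is (1.960 + 0.842) × √(2/115) = 0.37 SD, in keeping with the plan's description of modest to medium effects.

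**2. Why the shape tests are sensitive.** For a single variance, Var(s²) ≈ σ⁴(2 + κ)/n, where κ is excess kurtosis. Normal theory uses 2σ⁴/n. The understatement factor is r = (2 + κ)/2, and a nominal 5% test has true level 2Φ(−1.96/√r).

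| Excess kurtosis κ | r | True level |
|---|---|---|
| 0 | 1 | 5% |
| 1.5 | 1.75 | 14% |
| 7 | 4.5 | 36% |
| 21 | 11.5 | 56% |

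This shows the mechanism only. Growth-shape tests compare several means and covariances, so their level has to be simulated.

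**3. Simulated rejection of a true shape.** Inputs from the documents: N=230 and four waves (Section E, Cohort 2). Assumed: the distributions, a 5% chi-square criterion, the growth variances and the wave spacing.

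*Poisson-lognormal counts:* intercept-only truth, waves at 0, 5, 11 and 17 months, free residual variances, 600 trials per row.

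| Skewness | Intercept-only rejected | Linear rejected |
|---|---|---|
| Normal data | 5% | 5% |
| 1.1 | 10% | 12% |
| 1.6 | 15% | 18% |
| 2.1 | 23% | 22% |
| 3.4 | 37% | 46% |

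When these settings were refitted with growth covariance matrices held positive semi-definite (250 trials, a conservative version), intercept-only versus linear rejected 5% for normal data and 9%, 13%, 15% and 26% down the skewed rows.

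*Skewed marginals whose covariance fits the true shape exactly (Vale-Maurelli):* waves coded 0, 1, 2.5, 4 in 4-month units, 1,500 trials, Monte Carlo error about 0.6-1.3 points.

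| Truth; residual variances; test | Skew 1 | Skew 2 | Skew 3 |
|---|---|---|---|
| Linear; free; model fit | 9.5% | 22.9% | 45.5% |
| Linear; free; versus quadratic | 9.3% | 24.3% | 48.0% |
| Linear; equal; model fit | 16.6% | 47.9% | 82.7% |
| Linear; equal; versus quadratic | 11.3% | 34.1% | 64.4% |
| Intercept-only; free; model fit | 10.3% | 33.3% | 59.9% |
| Intercept-only; free; versus linear | 8.5% | 21.1% | 39.4% |

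Normal data gave 4.4-6.1%. Poisson-gamma counts (skew 1.1-2.9) gave 10.9-61.7% with free and 11.6-77.0% with equal residual variances. Independent skewed growth factors and errors (skew 1.4-2.2) gave 4.5-6.3% with free residual variances, which is no inflation, but 11.6-44.7% with equal ones.

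**4. Scaled tests.** In the first set, Satorra-Bentler difference tests stayed at 5-7%. In the second, at N=230, scaled model-fit tests rejected 4.4-7.9% (free) and 5.5-9.1% (equal), and scaled difference tests 5.1-9.0% (equal). With 20% loss (N=184) the worst case was about 10%.

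**5. The treatment test.** The null test of treatment on slope rejected 3.9-6.5% in every condition at N=230.

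**6. Power after an unneeded quadratic.** Assume 115 per arm, waves at 0, 5, 11 and 17 months, within-child correlation 0.5, and an arm gap rising linearly to 0.37 SD. The slope is 0.37/17 = 0.02176 per month. In the linear model Σ(t − 8.25)² = 162.75, so SE = √[(2 × 0.5/115)/162.75] = 0.00731, z = 2.98 and power is 85%. Generalised least squares with a quadratic term added gives:

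| Quantity tested in the quadratic model | z | Power |
|---|---|---|
| Linear coefficient, time zero at baseline | 0.02176/0.02627 = 0.83 | 13% |
| Linear coefficient, time centred at its mean | 0.02176/0.00736 = 2.96 | 84% |
| Linear and quadratic jointly (2 df) | – | 76% |
| Change from baseline to last wave | 0.37/0.1243 = 2.98 | 84.5% |
| Change from post-treatment to last wave | 2.11 | 56% |

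**The case against.** The strongest reply is that the documents fix none of the quantities that drive the size. The observed codes might be counts, rates, ratings or composites. Model fit might be judged by an index and not by a 5% chi-square test. Residual variances might be free, and in one skewed structure free variances removed the problem entirely. Only one of three Hypothesis 1 sources is in question; no case is made here about parent or teacher report. All of this stands, and it is why the result is conditional. The simulated range is neither a floor nor a ceiling for this trial.

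A reader might infer that the efficacy test itself is invalid. The documents and the calculation do not support that: allocation is close to 1:1 ("An approximately equal distribution of families will be assigned to each of the two conditions"), and the null treatment-on-slope test held its level throughout.

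A reader might also infer that power falls from 85% to 13%. That requires the linear coefficient to be tested alone with time zero at the first or last wave. The plan states no time coding and no such test. Its worked example concerns the amount of reduction over one year. Read as change from baseline to the last wave, that loses almost nothing; read as change from post-treatment onward, power is 56%.

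Finally, the rejection rates are for separate steps. How often the whole sequence would end at a quadratic was not computed.

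What the reply does not remove is that the plan names normal-theory methods, names no alternative for the shape step, and leaves open the settings under which that step can fail.

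**Conclusion.** The point holds in conditional form. The plan commits the growth models to normal-theory estimation and chooses their shape by tests that are sensitive to kurtosis. If the observed-behavior codes are skewed counts and shape is chosen by a 5% chi-square test, a true shape is rejected in roughly 10% of trials at skewness about 1. At skewness about 3 the figure is about 35-45% or more: lower in the constrained fits, much higher with equal residual variances. If the codes are close to normal, the effect is nil.

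The harm is a wrong statement about the pattern of change and a growth model more complex than the data warrant. It is not a false-positive treatment effect. Loss of power depends on which parameter is reported, and the plan should settle that too. The change is worth making before the observed codes are analysed, so that the estimator is not chosen after seeing results.

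**What to change.** In Section C, Data Analysis, replace the normal-theory wording with: *All regression, LGM and SEM models will use robust maximum likelihood (sandwich standard errors); growth-shape comparisons will use scaled chi-square and scaled difference tests.*

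Add: *Whatever growth shape is chosen, the arm effect will be the between-arm difference in model-implied change from baseline to 12-month follow-up.*

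State the significance level or fit criterion for the shape step and whether residual variances are free or equal. Optionally, add a negative binomial growth model as a sensitivity analysis for observed codes that are counts or mostly zero.

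The cost is a few sentences and an estimator option in standard SEM software, with no new data. The downside is that scaled tests remain slightly liberal at this sample size, at about 5-9%.
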